1. Objectives: Tourette's Syndrome (TS) is a neuropsychiatric disorder characterized by brief, repetitive movements and vocalizations called tics. The effects of TS in children and youth are far-reaching, with academic, occupational, and social implications. Current treatments for TS remain limited, both in scope and efficacy. Pharmaceuticals prescribed to control tics often have severe side effects with suboptimal benefit [1]. Behavior therapy has limited efficacy in children and is difficult for patients to access. Hence, there exists a salient need for the development of safe, accessible, and effective treatments for young people with TS. Indeed, a recent study has suggested that the maturational reduction in tic frequency that is sometimes seen in TS is due to a conscious effort directed at tic suppression, which develops over time. Tic suppression is associated with an increase in tonic inhibition in the supplementary motor area (SMA), and correlates with increased GABA neurotransmission and levels [2]. Consequently, the SMA is a direct target for therapeutic intervention. Repetitive transcranial magnetic stimulation (rTMS) involves a safe, non-invasive application of a magnetic field to a target brain area in order to change its activity and function. Our central hypothesis is that low frequency rTMS, targeted to the SMA, will reduce tic severity through the potentiation of cortical GABAergic neurotransmission. We propose the following **specific objectives**:

(Aim 1) **To characterize the effect of low frequency rTMS of the SMA on TS symptoms.** *We hypothesize that TS symptom severity (as measured by the Yale Global Tic severity Scale or YGTSS) will decrease with low frequency rTMS targeting the SMA.*

(Aim 2) **To identify TMS-mediated alterations in brain metabolites and functional connectivity that serve to normalize cortical activity.** *We further hypothesize that improvement in TS symptoms will be moderated by TMS-induced changes in GABA and glutamate in the SMA assessed with proton magnetic resonance spectroscopy (¹H MRS), potentiation of GABAergic neurotransmission assessed with short-interval cortical inhibition (SICI), and changes in the functional connectivity between the SMA and primary motor cortex.*

2. Background: Tics in TS are thought to arise from 1) dysregulation of excitation/inhibition in brain regions related to motor function, and 2) alterations in specific brain chemistry that potentiates overexcitability in the primary motor cortex (M1), via input from the SMA. This results in the activation of striatal neurons, and hyper-excitation of the M1, leading to the expression of tics. It is hypothesized that TS is also associated with a reduction in GABA transmission within the SMA and M1 [3]. One technique that has shown promise in normalizing brain function and reducing symptoms of TS in children and adults is rTMS. While initial experiences with varied approaches were not encouraging [4] [5] an effective approach is emerging [6] [7] [8]. Furthermore, it is not known what effects this technique has on the concentration of brain metabolites that mediate cortical hyperactivity and inhibitory neurotransmission. In this study, we aim to investigate whether low frequency rTMS can improve TS symptoms in a pediatric population, and what effects this technique has on the concentration of brain metabolites that mediate cortical hyperactivity.

3. Novelty (What will we learn that we don't already know?): The neurobiological study of the novel application of rTMS in pediatric TS allows us to map the trajectory of adaptive changes in the brains of children with TS, and to attempt to speed up these processes as they relate to decreasing cortical hyper-excitability, modulating GABAergic neurotransmission, increasing inhibitory metabolite levels within affected brain regions. Our multimodal approach allows us to gain critical insight into the structural, functional, and metabolic correlates of TS symptoms within the pediatric brain, an area that currently remains underexplored.

4. Methods

Sample: A pilot cohort of 11 males with TS (7-12 years, right handed, no comorbid ADHD) will be recruited through the Calgary Tourette Syndrome Clinic (Alberta Children's Hospital, Calgary, Alberta). Participants will continue prescribed medication regimes during the trial at the discretion of individual medical care professionals.

Measurements: To establish diagnosis and ascertain treatment response, we will conduct assessments at baseline, weekly during treatment (including the final week) and at 8 week and 6 month follow-ups. Measures used include the Yale Global Tic severity Scale (YGTSS), Present and Lifetime version of the Kiddie Schedule for Affective Disorders and Schizophrenia (K-SADS-PL), Multidimensional Anxiety Scale for Children, the Children's Depression Rating Scale-Revised, and the General Behavior Inventory (P-GBI).

MRI Acquisition: Participants will undergo both baseline and post-treatment MRI scans. MR data will be acquired on a GE 3T Discovery 750W scanner, and include a high-resolution anatomical scan for use in the rTMS procedure. Voxels within the M1 and SMA will be targeted by short echo (TE= 30msec, TR = 2000 msec) and MEGA PRESS proton magnetic resonance spectroscopy (1H-MRS) protocols. Analysis of MRS will be completed using the LCModel method, which converts the in vivo spectrum to a linear combination model for each metabolic solution [9, 10]. The SMA will be confirmed during the scan with a brief right and left finger tapping functional magnetic resonance imaging (fMRI) task [11]. We will also collect resting state fMRI and diffusion tensor imaging (DTI). Total time in the scanner is less than 60 minutes. Our established acquisition is well tolerated from ages 5 through adulthood.

Single and Paired-Pulse TMS (Neurophysiology): Using established lab protocols, the following motor neurophysiology measures (and their possible neurotransmitter system correlates) will be defined for M1 bilaterally at baseline and 1 week post-intervention: rest and active motor thresholds (RMT, AMT), stimulus response curve (100-150%RMT), short-interval intracortical inhibition (SICI, GABA_A), cortical silent period (cSP, GABA_B), ipsilateral silent period (iSP, interhemispheric inhibition), and intracortical facilitation (ICF, glutamatergic NMDA)[12].

Low-Frequency rTMS (Neuromodulation): Baseline T1 MR images will allow individualized neuronavigation (Brainsight 2, Rogue Research, Montreal QC) to coregister the rTMS Airfilm coil (Magstim, UK) precisely to the SMA as defined by fMRI. Interventional rTMS parameters will be: intensity 100% RMT, frequency 1Hz, duration 20 minutes (1200 stimulations). Treatments will occur on each weekday at the same time of day for three weeks (15 total).

Analysis: Statistical analyses will be performed using SPSS for Windows 22.0 (SPSS Inc., Chicago, IL). For aim 1, to test for differences in tic symptoms (YGTSS) with rTMS, a repeated measures analysis of variance (rmANOVA) will be performed. A similar approach will be used for assessing glutamate concentration in the SMA, SICI, ICF, CSP (Aim 2). Furthermore for Aim 2, functional connectivity changes with rTMS will be examined using Statistical Parametric Mapping (SPM) approaches. Pearson correlations between clinical and neurobiological variables controlling for age will be explored.

5. Sample size with justification: Estimating the sample size needed was based on similar studies. For the primary outcome measure (aim 1) of a reduction in tic severity (Yale Global Total Tic Severity Scale), we set $p < 0.05$ (two tailed), $d = 0.47$, power = 0.80, rendering a need for a minimum of 10 subjects. Clinically meaningful change in the YGTSS will be defined at a 23% or greater reduction in total score [13].

6. Anticipated Results: We predict this novel treatment will demonstrate reduction in tic severity and intrusiveness. Potential pitfalls include (1) intolerance to rTMS, (2) inadequate MRI data quality and (3) non-response to treatment. For TMS tolerability, most do very well, with a low incidence of side effects [14]. Moreover, low frequency rTMS is the most well tolerated type of rTMS. With regard to motion during the MR scan, our group has scanned over 200 subjects at the Alberta Children's Hospital to date. Data loss from motion accounts for less than 5%. To improve data quality, we have a mock scanner that helps acclimatize children to the scanning procedure. Given our collaboration with the Calgary Tourette Syndrome clinic, we anticipate robust recruitment (over 1,000 patients associated with the clinic).

7. Likelihood of Generating New Funding: In Canada, there are only 5 active operating CIHR grants with any conceptual relationship (however remote) with TS. Only two examine treatment (both behavioral interventions) and only one targets children, but simply as a sub-population. ClinicalTrials.gov has only two actively recruiting studies of TS listed in Canada as well (physical activity, pharmacological). **Despite the severity, prevalence, onset in childhood, and limitations of current interventions, there is little active research in TS in children.** Furthermore, despite the recent evidence described above implicating the SMA and indicating the promise of rTMS, no study is currently combining neurobiological measures with brain stimulation to target symptoms in TS. We believe, given our infrastructure and expertise, we are well suited to take leadership in this area internationally. Initial data will be applied to funding applications for the Thrasher foundation (\$300,000 over 3 years) and the Tourette Syndrome Association Research Grant (\$150,000 over 2 years). Similar funding will be sought from CIHR, AIHS, and NIH as appropriate. We have also formed a new collaboration with the Mayo Clinic, University of Cincinnati, CAMH, and others through our CAIRNS (Child and Adolescent International Research into Neuro-Stimulation) research program. This collaboration can help in developing larger scale trials.

Budget (How will the funds be spent? Include discussion of overlap with existing projects, if appropriate. Provide a justification and indicate the amount to be spent on each budget item).

Personnel

[Redacted personnel information]

Overlap

There is no overlap with existing projects. This direction into Tourette's Syndrome is entirely novel.

Please note that supplementary or "top-up" funding is not permitted for this competition; projects must explore a new avenue of research for the investigator.

Are there any other sources of funding? Yes: X - If yes, from where: [name] start up funds (\$4,950)

References:

1. Pringsheim T, et al; *Canadian journal of psychiatry Revue canadienne de psychiatrie* 2012, **57**(3):133-143.
2. Draper A, et al; *Current biology : CB* 2014, **24**(19):2343-2347.
3. Franzkowiak S et al; *PloS one* 2012, **7**(1):e27850.
4. Wile DJ; *Current treatment options in neurology* 2013, **15**(4):385-395.
5. Wu SW et al; *Brain stimulation* 2014, **7**(2):212-218.

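### Aims 1 and 2 are worded as effects of rTMS, but one treated cohort without a comparator can show only change from before to after rTMS

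*Combined protocol and SAP*

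**What the plan says.** **Aims.** Section 1 gives Aim 1 as "To characterize the effect of low frequency rTMS of the SMA on TS symptoms". The heading of Aim 2 calls the brain alterations TMS-mediated, and its hypothesis is that "improvement in TS symptoms will be moderated by TMS-induced changes in GABA and glutamate in the SMA". Section 2 adds "we aim to investigate whether low frequency rTMS can improve TS symptoms in a pediatric population", and section 6 says "We predict this novel treatment will demonstrate reduction in tic severity and intrusiveness".

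**Design.** Section 4, Sample: "A pilot cohort of 11 males with TS (7-12 years, right handed, no comorbid ADHD) will be recruited". One rTMS regimen is described. No sham, control, waiting-list, crossover, run-in or blinded rating is described.

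**Analysis.** Section 4, Analysis: "to test for differences in tic symptoms (YGTSS) with rTMS, a repeated measures analysis of variance (rmANOVA) will be performed". A similar approach is planned for glutamate, SICI, ICF and CSP. Connectivity is examined by SPM, and exploratory correlations control for age. No between-group factor or medication covariate is named.

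**Medication.** Section 4, Sample: "Participants will continue prescribed medication regimes during the trial at the discretion of individual medical care professionals". The plan does not say whether changes are logged.

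**Natural course.** Section 1 itself refers to "the maturational reduction in tic frequency that is sometimes seen in TS".

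**The concern.** The aims name a causal quantity, and the design estimates a different one. With a single treated group, the mean difference between visits is the sum of any rTMS effect, natural course, regression to the mean, placebo response or rater expectation, and any medication change. Nothing in the design separates the first term from the others. SPM and the correlations do not help, because they use the same uncontrolled cohort.

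What is at stake is the conclusion. If a significant time effect were taken as the answer to Aim 1 as worded, the trial would claim something that it cannot show. Section 7 says that the initial data will support funding applications, so the way the result is described will affect what follows.

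**Working it through.** **1. Aim against design.** The plan does not name the ANOVA factor. With one cohort, one regimen and no grouping variable, time is the only factor that its description supports. The point is structural and needs no figure. The steps below only indicate size.

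**2. The plan's own figure.** The plan gives no number on attribution. Its only figure for the Aim 1 test is the minimum of 10 subjects in section 5 (two-tailed 0.05, d = 0.47, power 0.80). Read as a paired t-test with d in SDs of the change score, d = 0.47 needs 38 subjects. A value of 10 arises only with inputs that are not stated, for example d on the raw SD with a before-after correlation of 0.9. That is a separate matter, and nothing here depends on it.

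**3. Inputs.** From the plan: n = 11, two-sided 5%, and assessments at baseline, three treatment weeks, 8 weeks and 6 months. That makes six occasions if the YGTSS is rated at each; section 4 does not say which occasions enter the ANOVA. Assumed: a true rTMS effect of zero and a nonspecific change of dz = 0.2 to 0.5 SD of the change score.

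**4. Two visits.** A two-level repeated measures ANOVA is equivalent to a paired t-test. The rejection probability comes from the noncentral t with 10 degrees of freedom, critical value 2.228 and noncentrality dz × √11.

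| dz | noncentrality | P(significant) |
|---|---|---|
| 0 | 0 | 0.050 |
| 0.2 | 0.663 | 0.092 |
| 0.3 | 0.995 | 0.147 |
| 0.5 | 1.658 | 0.323 |

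MRI is planned at baseline and post-treatment, and neurophysiology at baseline and one week post-intervention. For Aim 2, two occasions is therefore the planned layout.

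**5. Six visits.** Simulation with compound symmetry, r = 0.7, and the same step at every visit after baseline (40,000 trials per cell):

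| dz | uncorrected | Greenhouse-Geisser |
|---|---|---|
| 0 | 0.051 | 0.026 |
| 0.2 | 0.078 | 0.043 |
| 0.3 | 0.123 | 0.074 |
| 0.5 | 0.301 | 0.206 |

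The corrected test is conservative at this sample size, so its values should be compared with about 0.025 and not with 0.05.

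**6. Medication change.** Assume that 2 or 3 of the 11 children shift by 1 SD of the change score, all in the same direction. The mean then moves by 2/11 = 0.18 or 3/11 = 0.27 SD. Simulated rejection rates:

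- Two-visit paired test: 0.065 and 0.095.
- Six visits, Greenhouse-Geisser, shift from the first weekly rating: 0.033 and 0.050.
- Six visits, Greenhouse-Geisser, shift from week 8: 0.036 and 0.061.

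In the six-visit layout this is about 3% to 6%, against a null rate of about 2.5%. If two children improve and one worsens by 1 SD, the two-visit rate is about 3.5%.

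**7. Responder proportion.** Section 5 defines clinically meaningful change as a fall of 23% or more. For an illustrative 5 of 11 children, the exact (Clopper-Pearson) limits are the 0.025 quantile of Beta(5, 7) = 0.167 and the 0.975 quantile of Beta(6, 6) = 0.766. The interval is 17% to 77%.

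**The case against.** **The aims can be read as before-after change.** The Aim 1 hypothesis sentence says only that severity will decrease with rTMS, and the analysis sentence is similar. No section states a rule for what will be concluded. This stands in part. A reader might infer that the investigators will announce a causal effect, but the documents do not say so. The Aim 1 heading and the Aim 2 wording still go beyond before-after change.

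**A single arm is ordinary for a pilot.** This stands. Section 7 presents the results as initial data and says that a collaboration can help in developing larger trials. A reader might infer that the design or the ANOVA is invalid, or that a control arm must be added. Neither follows, because the ANOVA is sound for change over time.

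**The medication element rests on silence.** This largely stands. Section 4 says that regimes continue. Clinicians' discretion allows changes, but none is said to be expected. A reader might infer that changes go unrecorded. A short funding application does not show that, and the effect in step 6 is small.

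**Maturation is a weak rival over three weeks.** This is fair for the treatment period, and less so at the 6-month visit.

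**Conclusion.** The concern holds as a mismatch between the wording of the aims and what the design can estimate. A significant time effect would show that ratings changed. It would not by itself show that rTMS changed them. This does not depend on any assumed number.

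The size is illustrative only, since the documents supply no nonspecific change, SD or within-child correlation. With no rTMS effect and a nonspecific change of 0.2 to 0.5 SD of the change score, significance occurs in 9% to 32% of two-visit tests and about 4% to 21% of six-visit Greenhouse-Geisser analyses. At the low end the inflation is slight.

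The stronger reading that unrecorded medication changes threaten the result is not supported. The documents do not show that a log is absent, and the assumed scenarios give about 3% to 6% for six visits with the correction. That part is a request for clarification. The rewording should be made, because it changes what the trial may conclude.

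**What to change.** 1. State Aims 1 and 2, and the conclusions drawn from them, as change from before to after rTMS, not attributable to rTMS without a controlled comparison. Present the results as pilot data for a later controlled trial. Replace the TMS-mediated and TMS-induced wording of Aim 2 in the same way.
2. Report the proportion of children with a 23% or greater YGTSS reduction descriptively, with an exact 95% confidence interval.
3. As a minor clarification, state that the date and type of any tic-medication change from baseline to 6 months will be logged and reported alongside the results, with no change to clinical care.

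No additional model is needed. Setting ratings after a medication change to missing could itself introduce bias if changes follow tic severity, and a difference between two fits in 11 children would be hard to interpret.

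The cost is a more modest conclusion and, if no log is kept now, one log field. No extra participants, visits or procedures are needed, and the planned ANOVA stays as it is.

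### The plan does not say that a child who stops rTMS early is still rated on the YGTSS in weeks 1 to 3, so the Aim 1 result may come from completers only

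*Combined protocol and SAP*

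**What the plan says.** Section 4 (Methods) of the combined protocol and SAP gives the only rating schedule. In Measurements: "we will conduct assessments at baseline, weekly during treatment (including the final week) and at 8 week and 6 month follow-ups". The rTMS paragraph sets the course at 15 weekday sessions over three weeks. The 8-week and 6-month visits are listed without any condition on treatment.

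The Aim 2 measures have their own timing. For imaging, "Participants will undergo both baseline and post-treatment MRI scans". The neurophysiology measures "will be defined for M1 bilaterally at baseline and 1 week post-intervention".

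The Analysis paragraph says that "Statistical analyses will be performed using SPSS for Windows 22.0" and that, for Aim 1, "to test for differences in tic symptoms (YGTSS) with rTMS, a repeated measures analysis of variance (rmANOVA) will be performed". It does not name the time points in the model, the children who form the analysis set, or the handling of a missing rating.

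Section 6 (Anticipated Results) foresees that some children may not tolerate the intervention: "Potential pitfalls include (1) intolerance to rTMS, (2) inadequate MRI data quality and (3) non-response to treatment". It then describes tolerability as good, without a rate. It gives no rule for the data of a child who stops.

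**The concern.** Two gaps meet here. The Measurements wording leaves open whether a child who is no longer receiving rTMS is still rated in the remaining treatment weeks. The Analysis paragraph names a method whose usual SPSS implementation needs a complete row for each child. If the first gap is settled by not rating the child, the second can remove him from the Aim 1 test.

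The children lost in this way would be selected by how they tolerated the intervention. The mean tic change would then describe those who tolerated 15 sessions, not all who started. In a cohort of 11 with no control arm described, one or two children can move the estimate visibly. Section 7 says that the initial data will go into funding applications, so a distorted estimate could be carried into the planning of larger trials.

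Part of this is a collection problem. An analysis method can retain a child with some ratings missing, but it cannot recreate week 2 and week 3 ratings that nobody took.

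**Working it through.** **Inputs.** Planned cohort: 11 (section 4, Sample). Stated minimum: 10 subjects, from two-sided 0.05, d = 0.47 and power 0.80 (section 5). Course: 15 sessions over three weeks, so five a week (section 4). Rate of early stopping: not given, so assumed below.

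**Step 1: follow one early stopper through the schedule.** Suppose a child stops after session 4, in week 1.

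- On a literal reading of Measurements he may have a week 1 rating, and has none in week 2, in week 3 or as the final-week rating.
- On a calendar reading he is rated in weeks 1, 2 and 3 like everyone else. The text does not choose between the two.
- On either reading the 8-week and 6-month ratings remain due.
- If the model includes the final-week visit and the literal reading applies, SPSS by default excludes him. If the model compares, say, baseline with 8 weeks, he stays in.

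**Step 2: effect on the estimated mean change.** Let completers improve by D on average, let k of 11 children stop, and let stoppers improve by rD. Then

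all-treated mean = [(11 − k)D + k·rD] / 11 = D·[11 − k(1 − r)] / 11,

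and completer mean ÷ all-treated mean = 11 / [11 − k(1 − r)].

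| Stoppers k | r = 0 (no change) | r = 0.5 (half as much) | r = 1 (equal) |
|---|---|---|---|
| 1 | 11/10 = 1.10 | 11/10.5 = 1.05 | 1.00 |
| 2 | 11/9 = 1.22 | 11/10 = 1.10 | 1.00 |
| 3 | 11/8 = 1.38 | 11/9.5 = 1.16 | 1.00 |

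If r exceeded 1, the ratio would fall below 1 and the completer mean would understate the change.

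**Step 3: how often children might be lost.** For an assumed stopping rate p, independent between children, P(at least one of 11) = 1 − (1 − p)^11, and P(two or more) = 1 − (1 − p)^11 − 11p(1 − p)^10.

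| Assumed p | P(at least 1) | P(2 or more, so fewer than 10 remain) |
|---|---|---|
| 2% | 0.20 | 0.02 |
| 5% | 0.43 | 0.10 |
| 10% | 0.69 | 0.30 |
| 20% | 0.91 | 0.68 |

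**Step 4: how much the threshold of 10 means.** The stated minimum does not follow from d = 0.47 read as a paired standardised effect. The normal approximation gives ((1.960 + 0.842)/0.47)² = 35.5, so 36 children, and the exact paired t calculation gives 38. A figure of 10 can be reached only with assumptions that the plan does not state, for example 0.47 read as Cohen's f with two time points and a correlation of 0.6. That is a separate matter. If 80% power at 10 children is nevertheless taken at face value (a paired effect of about 1.00), power is 0.845 with 11 children, 0.80 with 10 and 0.745 with 9. The loss of power is modest. The change in who is being described matters more.

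**The case against.** The strongest reply is that the schedule is naturally read as a calendar. The course is fixed at three weeks, so weekly ratings through the final week mean weeks 1, 2 and 3. Nothing in the documents withdraws an early stopper or cancels his visits. This stands as far as it goes: the text is silent, and staff could well keep rating the child. It does not remove the ambiguity, which would be settled ad hoc once a child had stopped.

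A reader might infer that outcome collection as a whole depends on being on treatment, or that an early stopper necessarily drops out of the Aim 1 test. The documents support neither. The two follow-up visits are unconditional, and exclusion depends on time points and missing-data handling that the plan does not state.

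A reader might also infer that the completer result must look too favourable. That needs stoppers to improve less than completers. Section 6 lists intolerance and non-response as separate pitfalls, and a child could stop for discomfort while his tics improve.

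It can also be said that a mixed model would keep the child through his baseline and follow-up ratings. That is right, and it is part of the fix, but it does not supply the missing end-of-treatment rating.

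Finally, one might want the second MRI and the neurophysiology moved to a fixed calendar point too. The documents give a reason not to. Aim 2 concerns changes induced by TMS, and timing neurophysiology from the end of the intervention holds the interval since stimulation constant. A fixed point would measure the child who stopped after session 4 about two weeks later after his last stimulation than the completers.

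**Conclusion.** The concern holds as a risk left open by the plan, not as a certain loss of data. A completers-only Aim 1 result arises if three things coincide: a child stops early, he is not rated in the remaining treatment weeks, and the final-week visit is in an rmANOVA that drops incomplete cases. The plan rules out none of the three, and names intolerance as its first pitfall.

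The size cannot be fixed from the documents. The overstatement of 10% to 38% for one to three stoppers is the case of no change in stoppers. It falls to 5% to 16% if they improve half as much, and vanishes if they improve equally. The stopping rates are assumptions, and the wording of section 6 suggests the lower end of the range. Falling below 10 analysed children should carry little weight, because that minimum is not reproduced from the stated inputs. The gap is still worth closing, because ratings not taken in weeks 2 and 3 cannot be obtained later.

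**What to change.** In section 4, Measurements, state that the YGTSS is rated at weeks 1, 2 and 3 counted from the first rTMS session, and at both follow-ups, for every child who received at least one session, whether or not rTMS continues.

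In section 4, Analysis, make all treated children the Aim 1 analysis set and name the time points in the model. Use a method that keeps children with incomplete ratings, such as a mixed model. Report how many children stopped and at which session.

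Leave the MRI and neurophysiology timing as it is, and report each child's interval since the last session.

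The cost is a few sentences and no new type of visit. A few families will be asked to attend after stopping rTMS, and the estimated mean change may be slightly smaller. The visible documents do not itemise visit costs, so the effect on the budget cannot be checked.

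### Spectra are acquired in SMA and M1 at both scans, but the only named metabolite test is pre-post SMA glutamate, with no M1 comparison or reference metabolite to expose a measurement shift

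*Combined protocol and SAP*

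**What the plan says.** Section 4, MRI Acquisition, sets two time points: "Participants will undergo both baseline and post-treatment MRI scans". It places spectroscopy in two regions: "Voxels within the M1 and SMA will be targeted by short echo (TE= 30msec, TR = 2000 msec) and MEGA PRESS". Quantification is stated without naming a region or a metabolite: "Analysis of MRS will be completed using the LCModel method".

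Section 4, Analysis, gives the YGTSS a repeated-measures ANOVA and then extends it: "A similar approach will be used for assessing glutamate concentration in the SMA, SICI, ICF, CSP (Aim 2". SMA glutamate is the only metabolite in that list. The one other analysis that could take in M1 spectra is exploratory and does not list its variables: "Pearson correlations between clinical and neurobiological variables controlling for age will be explored".

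Aim 2 in section 1 places the metabolite hypothesis in the SMA: "TMS-induced changes in GABA and glutamate in the SMA assessed with proton magnetic resonance spectroscopy". Section 2 gives M1 a role of its own, hypothesising that "TS is also associated with a reduction in GABA transmission within the SMA and M1". It also describes M1 overexcitability as arising through input from the SMA.

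Section 4, Sample, describes a single cohort of 11 boys. No sham or untreated group, phantom check, scan-rescan check or reference-region check is described.

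**The concern.** The named metabolite test compares one region at two time points in one treated group. It cannot distinguish a change at the stimulated site from anything that moves the measurement in the same direction, in most children, between the first and second scan. A change in acquisition or processing software is one example; children being more settled at their second scan is another.

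Data that could partly separate these explanations are already planned: the M1 voxel, and the other metabolites fitted in the same SMA spectra. The plan gives neither a role in interpreting the SMA result.

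What is at stake is the mechanistic claim of Aim 2. Section 7 says the initial data will go into funding applications, so a non-specific shift reported as an SMA effect would be carried into later work.

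**Working it through.** **Inputs from the documents.** n = 11 (section 4, Sample); two scans; two-sided 5% level (section 5, where it is stated for the YGTSS and is carried over here). The plan has no sample-size or precision figure for any MRS outcome. Its minimum of 10 subjects concerns the YGTSS and does not bear on this point.

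**Assumptions.** There is no true rTMS effect. A systematic shift δ is common to the children and expressed in SDs of the within-child pre-to-post change. The documents give no MRS SD or drift, so a range is shown.

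**Step 1: the SMA-only test.** With two time points, the repeated-measures ANOVA is the paired t-test (F = t²) on 1 and 10 degrees of freedom. The rejection probability is P[F′(1, 10, λ) > F₀.₉₅(1, 10)], with λ = n·δ².

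| δ (SD of change) | λ = 11·δ² | Rejection rate, no true effect |
|---|---|---|
| 0 | 0 | 5% |
| 0.25 | 0.69 | 12% |
| 0.5 | 2.75 | 32% |
| 0.75 | 6.19 | 61% |
| 1.0 | 11.0 | 85% |

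In percentage terms, with an assumed SD of change of 10%, a 2.5% shift is δ = 0.25 (12%) and a 5% shift is δ = 0.5 (32%). With an assumed SD of 6%, a 5% shift is δ = 5/6 = 0.83, and the test rejects in about 70% of trials.

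**Step 2: the SMA-minus-M1 contrast.** On the log scale, a proportional shift common to both voxels subtracts out, and the test stays at 5%. A shift that differs between voxels does not cancel.

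**Step 3: what the contrast costs.** Let the SMA effect be e (in SDs of change), let M1 respond by a fraction k of it, and let the two regional changes have equal SD and correlation ρ. The contrast has standardised effect e(1 − k)/√[2(1 − ρ)].

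- M1 does not respond (k = 0), e = 0.94, for which the SMA test alone has 80% power: contrast power is 51%, 66%, 80% and 95% for ρ = 0, 0.3, 0.5 and 0.7.
- e = 1.0, ρ = 0.5, so the denominator is 1: power is 85% for k = 0, 32% for k = 0.5 (standardised effect 0.5) and 5% for k = 1.

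**Step 4: how well a negative control can show stability.** The 95% interval for a mean change at n = 11 has half-width 2.228/√11 = 0.67 SD of that metabolite's change. A non-significant result therefore does not establish stability; the interval has to be reported.

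**The case against.** Several arguments on the other side have force.

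- **M1 spectra may be used.** A reader might infer that they enter no analysis at all. The documents do not support that: the exploratory correlations leave their variables open, and the LCModel statement names no region. What stands is that no test of M1 change and no regional comparison is named. A correlation with clinical scores would not remove a mean shift in any case.
- **The shift is hypothetical.** Only a shift that is systematic across children biases the test. Coil loading and day-to-day calibration may vary by session and so add to the SD rather than move the mean. Concentration referencing, which the plan does not describe, may remove some global effects. This stands: the documents do not show that a shift is likely, and the figures say only how vulnerable the test is if one occurs.
- **M1 is not a clean control.** A reader might infer that an M1 contrast restores a valid test, or that equal change in both regions shows artefact. Neither follows. The contrast removes only shifts common to both voxels, and under section 2's own model M1 may respond through SMA input. Step 3 shows how much power that could cost.
- **Aim 2 claims change in the SMA, not change confined to it.** This is correct, and it is why the contrast belongs beside the SMA test as a secondary check.
- **The root problem is the uncontrolled design,** which affects YGTSS and the neurophysiology too. This is also correct; the spectra can address only part of it, for a secondary aim in a pilot.

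A reader might also infer that the M1 spectra come from the same tissue as SICI, ICF and the silent period. The neurophysiology is bilateral and the side and size of the M1 voxel are not given, so that cannot be said.

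**Conclusion.** The concern holds in a limited form. The plan names a pre-post test of SMA glutamate and no analysis that would reveal a measurement shift, although spectra suited to a partial check are already planned. If a systematic shift of 0.25, 0.5 or 1.0 SD of the within-child change occurred with no true effect, the test would be significant in about 12%, 32% or 85% of trials rather than 5%. This rests on n = 11, a two-sided 5% level, and an assumed shift in the same direction across children. The size and likelihood of any such shift are unknown from the documents.

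The finding concerns how an Aim 2 result may be interpreted. It does not show that the SMA test should be replaced, or that a positive result would be false.

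**What to change.** Amend the Analysis paragraph of section 4 as follows.

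1. Keep the pre-post SMA glutamate test as planned.
2. Report the M1 glutamate change beside it, both with estimates and 95% confidence intervals.
3. Prespecify the region (SMA, M1) by time (baseline, post-treatment) term on the log scale as a secondary specificity check only.
4. Report the pre-post change in one metabolite not hypothesised to change, from the same SMA spectra, as a negative control (for example NAA, water-scaled). State the concentration reference, and judge stability from the interval.
5. Fix the reading in advance. If the negative control shifts, do not attribute the SMA glutamate change to rTMS. If it is stable and SMA and M1 change alike, report that the change is not shown to be SMA-specific, noting that M1 may respond through SMA input.
6. State that without a control group a pre-post metabolite change cannot be firmly attributed to rTMS.

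A related gap to close in the same edit: GABA is in the Aim 2 hypothesis but absent from the repeated-measures list.

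The cost is wording and a few more secondary tests; the scans and voxels are already planned. The contrast cancels only shifts common to both voxels, and it loses power if M1 responds: from about 85% to 32% for a 1.0 SD SMA effect with half the response in M1 and correlation 0.5. The negative control can miss a shift specific to glutamate.
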